Study Protocol and Statistical Analysis Plan:

Evidence of the Advantages of Preoperative Intra-aortic Balloon Pump in Surgical Revascularization of Acute Myocardial Infarction

Brief Title: Use of Intra-aortic Balloon Pump Before Surgery for Acute Myocardial Infarction

NCT number: NCT06468982

Document date: May 1, 2021

Evidence of the Advantages of Preoperative Intra-aortic Balloon Pump in Surgical Revascularization of Acute Myocardial Infarction

Patients hospitalized due to acute myocardial infarction (AMI) and scheduled for coronary artery bypass grafting (CABG) surgery based on the decision of the Cardiology and Cardiovascular Surgery council will be included in this prospective observational cohort study. Based on their clinical conditions, the patients will be categorized into two groups: Group A, comprising those receiving intra-aortic balloon pump (IABP) support, and Group B, comprising those not receiving IABP support.

The patients' anamnesis, medical history, physical examination findings, laboratory results, and EuroScore-II scores will be meticulously recorded. Details of the assessments are as follows:

Assessment of Chest Pain (Angina): Chest pain severity will be evaluated on the first day of admission using a scoring system based on the Wong-Baker FACES® pain scale (0–10; Wong-Baker FACES Foundation; https://wongbakerfaces.org). For patients in the IABP group, pain severity will also be recorded immediately before IABP placement and at 12 and 24 hours post-implantation.

Laboratory Studies: The following parameters will be analyzed: hemoglobin (g/dL), hematocrit (%), platelet count, troponin (ng/mL), CK-MB (U/L), LDL (mg/dL), C-reactive protein (CRP, mg/L), glycated hemoglobin (HbA1c, %), and creatinine (mg/dL). High-sensitivity cardiac troponin I (hsCTI) levels will be measured, with the reference range of 0–0.04 ng/mL for both genders, as per our hospital's laboratory standards. hsCTI levels will be checked at admission and subsequently every 24 hours for both groups until the patient undergoes surgery.

Echocardiography (ECHO): On the first day, ECHO will be performed to assess ventricular function, ejection fraction (EF%), valve pathologies, and any ventricular abnormalities such as aneurysm or ventricular septal rupture. Follow-up ECHO will be conducted during the early postoperative period and at the first-month follow-up after discharge to reassess EF% and identify any pericardial effusion.

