- · Patients presenting with acute cardiogenic shock or cardiac arrest

Preoperative IABP Application and Indications:

The primary indications for intra-aortic balloon pump (IABP) application in patients include elevated troponin levels and recurrent or persistent chest pain at rest.

Other common indications are:

- Hemodynamic instability.
- Multivessel coronary artery disease.
- Left main coronary artery disease.
- Narrow and/or tortuous coronary artery anatomy where percutaneous coronary intervention (PCI) has failed or is not feasible.

Procedure:

The IABP catheter is typically inserted into the femoral artery by cardiovascular surgeons under local anesthesia. The placement of the catheter is confirmed either in a hybrid operating room or using a portable imaging scope.

Statistical Analysis

The research will be conducted utilizing IBM SPSS 24 (IBM, Armonk, NY, USA) software and R-project version 4.2.3 for statistical analysis. The statistics will be provided in terms of mean, standard deviation, median, minimum, maximum, percentage, and count. After testing for normality, baseline characteristics of the two groups will be compared using Student's t-test or the Mann–Whitney U-test for continuous variables and chi-square or Fisher's exact tests for categorical variables. Differences between the IABP group and the control group regarding repeatedly measured outcomes will be analyzed using mixed ANOVA. The prognostic value of risk factors for in-hospital mortality will be evaluated by multivariate logistic regression analysis. The propensity score will be computed using a logistic regression model, incorporating the following covariates: age, gender, creatinine, CK-MB, hs-CTI levels, preoperative LVEF, and EuroScore II. The statistical significance level will be set at p<0.05.

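### As written, no outcome analysis is stated to use the propensity score, and the score omits by name rest pain, left main disease and hemodynamic instability, all listed reasons for an IABP

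*Combined protocol and SAP*

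**What the plan says.** The study is an observational cohort. The opening description forms the groups by clinical judgment: "Based on their clinical conditions, the patients will be categorized into two groups".

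The section on IABP indications gives as primary reasons "elevated troponin levels and recurrent or persistent chest pain at rest". Among its other reasons are "Hemodynamic instability" and "Left main coronary artery disease", along with multivessel disease and unsuitable anatomy where PCI failed or was not feasible.

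The Statistical Analysis section has three sentences that bear on the comparison:

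- Repeated outcomes: "Differences between the IABP group and the control group regarding repeatedly measured outcomes will be analyzed using mixed ANOVA". No covariates are named.
- Mortality: "The prognostic value of risk factors for in-hospital mortality will be evaluated by multivariate logistic regression analysis". The risk factors are not listed, and neither IABP nor the score is named.
- The score: "The propensity score will be computed using a logistic regression model". The same sentence then fixes its seven terms: "incorporating the following covariates: age, gender, creatinine, CK-MB, hs-CTI levels, preoperative LVEF, and EuroScore II". No matching, weighting, stratification or adjustment follows.

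The two-group tests (t, Mann–Whitney, chi-square, Fisher) are assigned to baseline characteristics only.

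**The concern.** If the device goes to patients judged to need it, a difference between groups in the hs-CTI course or in EF% can reflect who was selected rather than what the device did. The propensity score is the natural protection against this, and the plan leaves two gaps in it. It does not say where the score enters. And the score as listed lacks three indications that can plausibly differ between the groups, one of them primary. Because the use is left open, it could also be chosen after the results are seen.

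Two related points add to this. hs-CTI is measured at admission and every 24 hours until surgery, but the plan does not say which value goes into the score; a value taken after IABP placement would not be a baseline covariate. Recurrent pain also acts twice: it is a reason for an IABP, and it leads to CABG, which ends the hs-CTI series.

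**Working it through.** **Step 1. Indications against score covariates.** The plan states no sample size, effect size or event rate, so it has no figure to reproduce. The first check is a comparison of two lists.

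| Listed indication | In the score by name? |
|---|---|
| Elevated troponin (primary) | Yes, as hs-CTI, time point not given |
| Rest pain (primary) | No, although pain severity is scored on day 1 |
| Hemodynamic instability | No; narrowed, not removed, by excluding shock and arrest |
| Left main disease | No |
| Multivessel disease | No, but may differ little among patients selected for CABG |
| PCI failed or not feasible | No, same remark |

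One of six is present by name. Of the five absent, three can plausibly differ between the groups.

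**Step 2. Possible size for a repeated outcome.** All inputs are assumed, one omitted indication at a time. In the group-by-time term, bias in SD = (p1 − p0) × d. Here p1 and p0 are the indication's prevalence in the IABP and control groups, and d is its effect on the change. An indication that shifts every time point equally has d = 0 and gives no bias.

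- Gap 0 to 0.30, d 0.3 to 0.8: bias 0 to 0.30 × 0.8 = 0.24 SD.
- If the listed covariates and the exclusions carry half the gap: 0 to 0.15 × 0.8 = 0.12 SD.

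False-positive rate of a two-sided 5% test (noncentral t, no true effect):

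| Bias | 50 per group | 100 per group |
|---|---|---|
| 0.10 SD | 7.9% | 10.8% |
| 0.12 SD | 9.1% | 13.5% |
| 0.24 SD | 22.1% | 39.3% |

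**Step 3. Mortality, if an IABP contrast is made at all.** The risk ratio is multiplied by [1 + (RR − 1)p1] / [1 + (RR − 1)p0]. With assumed RR 1.5 to 3, control-group prevalence 5% to 40% and a gap of 0 to 30 points, the factor runs from 1.00 to 1.7/1.1 = 1.55. At half the gap the maximum is 1.4/1.1 = 1.27.

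**Step 4. What adding the indications does.** This is a simulation with assumed inputs: no IABP effect, left main gap of about 20 points, 0.5 SD effect on change, and the seven covariates independent of left main disease. The adjusted analyses use overlap weights. The 11-term score adds a pain score, rest pain, left main disease and hemodynamic status. Bias in SD, 50 / 100 per group:

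| Effect of each of the seven covariates on outcome | Unadjusted | 7 terms | 11 terms |
|---|---|---|---|
| None | 0.104 / 0.098 | 0.108 / 0.102 | 0.003 / −0.002 |
| 0.2 SD | 0.295 / 0.286 | 0.107 / 0.103 | 0.004 / −0.001 |

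The 0.10 SD left by the seven terms is 0.20 × 0.5, as in Step 2. How much those seven terms remove depends entirely on how well they predict the outcome. The same is true of precision. With no covariate effect, the 11-term standard error exceeds the unweighted one (0.228 against 0.206; 0.153 against 0.144). With 0.2 SD each, it is slightly lower (0.223 against 0.230; 0.157 against 0.162).

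If a trigger of similar size arises after admission, the 11-term score still leaves 0.107 / 0.109 SD (run with no covariate effect).

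**The case against.** The strongest reply is that silence is not a decision. A score described beside the outcome analyses was presumably meant to be used, and the mortality model has unlisted factors, so it may contain IABP or some indications. This stands: a reader might infer that the comparison will be unadjusted, but the documents support only that it is not stated to be adjusted.

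Second, the plan already does part of the work. Troponin, the primary indication closest to the hs-CTI outcome, is in the score. The exclusions (shock or arrest, mechanical complications, iatrogenic injury, renal failure, peripheral arterial disease, prior cerebrovascular accident) aim at homogeneous risk. EuroScore II, LVEF and CK-MB may carry some of the missing indications. This also stands, though the documents do not show how much, and no exclusion concerns rest pain or left main disease.

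Third, a reader might infer from the first simulation row that using the existing score gains nothing, or that a longer score must cost precision. Neither follows. The second row shows the existing score removing most of the bias, with no loss of precision from the longer one, and nothing in the documents says which row is closer to the truth.

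Fourth, a reader might infer that the plan is tilted toward a false benefit. The documents do not support that. If the IABP group holds more unstable or left main patients, an unadjusted mortality comparison would be biased against the device, and for hs-CTI the direction is unknown.

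**Conclusion.** The point holds in this form. Allocation is by clinical condition, no outcome analysis is stated to use the propensity score, and the score omits by name one of the two primary indications together with left main disease and hemodynamic instability. Carrying out the plan exactly as worded would leave confounding by indication in the main comparison, and applying the listed score would reduce it to an unknown degree.

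The size cannot be derived from the documents. The illustrations run from no bias to 0.24 SD for a change and from 1.00 to 1.55 for a mortality risk ratio. They rest on assumed prevalences, effects and group sizes, and take one indication at a time. The text findings do not depend on them. This is a cheap improvement.

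**What to change.** Amend the Statistical Analysis section as follows.

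1. State that the main IABP versus control comparisons, including the repeated-measures analysis and mortality, use the propensity score with IABP as a named term, by one method fixed in advance. Overlap weighting is one acceptable choice: a weighted regression with group, time and group-by-time terms, and robust standard errors clustered by patient. Show unadjusted results alongside.
2. Use admission values from before IABP placement for all covariates, including hs-CTI.
3. Add the admission Wong-Baker score (or rest pain at admission), left main disease, and admission hemodynamic status with a definition set in advance. Add multivessel disease and PCI failed or not feasible in one sensitivity analysis.
4. Report standardized mean differences before and after adjustment. Overlap weights from a logistic score balance the means of included terms by construction, so these differences inform mainly on the variables left out.
5. State two limitations: pain or instability arising after admission is not captured, and recurrent pain leads to CABG and so ends the hs-CTI series.

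The cost is SAP wording, coding of left main disease from the angiogram, coding of hemodynamic status (and of rest pain, if used) from the admission record, and one definition. The downside is more terms with no stated sample size. With an assumed 50 IABP patients, patients per term fall from 50/7 = 7.1 to 50/10 = 5.0, or to 50/11 = 4.5 if both pain variables are used. With 100 they fall from 14.3 to 10.0 or 9.1. Intervals may widen where overlap is poor. With overlap weights the effect applies to patients with overlapping characteristics, not to all IABP patients.

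### The propensity score names one of the six stated IABP indications (troponin), so comparisons that use it may keep confounding by indication

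*Combined protocol and SAP*

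**What the plan says.** The opening description of the combined protocol and SAP sets out an observational cohort of patients with acute infarction who are already "scheduled for coronary artery bypass grafting (CABG) surgery based on the decision" of a joint council. Assignment is not random: "Based on their clinical conditions, the patients will be categorized into two groups", with and without IABP.

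The section Preoperative IABP Application and Indications gives the primary indications as "elevated troponin levels and recurrent or persistent chest pain at rest". It then adds "Hemodynamic instability", "Multivessel coronary artery disease", "Left main coronary artery disease", and narrow or tortuous anatomy in which "percutaneous coronary intervention (PCI) has failed or is not feasible". Counting the two primary ones separately, that makes six.

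The Statistical Analysis section fits the propensity score by logistic regression, "incorporating the following covariates: age, gender, creatinine, CK-MB, hs-CTI levels, preoperative LVEF, and EuroScore II". It does not say how the score will be used or for which outcomes. Repeated outcomes go to mixed ANOVA. A logistic regression for in-hospital mortality is planned, but its variables are not listed.

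On available data, a chest-pain score is taken on day 1 in all patients. Scores just before placement and at 12 and 24 hours afterwards are scheduled in Group A only. hs-CTI is measured at admission and then every 24 hours until surgery in both groups. Angiography guides the grafting, but angiographic findings are not among the items listed for recording.

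**The concern.** A propensity score balances only what is in it, or what is closely tracked by what is in it. Here the protocol writes down the reasons for giving an IABP, and the treatment model leaves most of them out. Following the stated list exactly could leave the groups different in ischemic severity and coronary anatomy.

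The outcomes at stake are those measured once per patient: ventilation time, bleeding, ICU stay, hospital stay, low cardiac output syndrome (LCOS) and in-hospital mortality. If the omitted indications worsen these, a score-based comparison is pushed against IABP, towards a masked benefit or an apparent harm. For hospital stay the direction is uncertain, because recurrent pain leads to surgery and may shorten the wait.

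A smaller, related gap is that neither hs-CTI nor CK-MB has a stated time point in the score. hs-CTI is measured serially, and the plan also wants to judge the effect of IABP on troponin, so a value taken after insertion would be a post-treatment variable.

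**Working it through.** **1. Indications against covariates.**

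| Stated indication | Named in the score? | Possible partial cover |
|---|---|---|
| Elevated troponin (primary) | Yes, as hs-CTI, time point not given | CK-MB |
| Recurrent or persistent rest pain (primary) | No | Not shown |
| Hemodynamic instability | No | Exclusions; perhaps LVEF, EuroScore II |
| Multivessel disease | No | Not shown; may vary little in a CABG cohort |
| Left main disease | No | Not shown |
| Difficult anatomy with PCI failed or infeasible | No | Not shown; may vary little in a CABG cohort |

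Named: 1 of 6. Not named: 6 − 1 = 5, including one of the two primary indications. The documents do not give the components of EuroScore II, so its coverage cannot be checked from them.

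**2. Do the exclusions close the gap?** Excluding shock or arrest at presentation narrows instability. Excluding mechanical complications, and emergency surgery for injury caused by angiography, may narrow it further. Lesser instability stays eligible. No exclusion is directed at rest pain, left main disease or multivessel disease.

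**3. Bias from one omitted binary indication.** The plan gives no sample size, event rate or effect size, so there is no figure to reproduce. Let p1 and p0 be the prevalence of the indication with and without IABP that remains after adjustment, and RR its effect on a binary outcome. The risk ratio is then multiplied by

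(1 + p1(RR − 1)) / (1 + p0(RR − 1)).

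All inputs are assumed:

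- 40% vs 30%, RR 1.5: 1.20/1.15 = 1.04
- 60% vs 30%, RR 2: 1.60/1.30 = 1.23
- 80% vs 20%, RR 3: 2.60/1.40 = 1.86

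**4. Illustrative simulation, continuous outcome, no true IABP effect.** There were 1,000 runs for each of 72 scenarios, with Monte Carlo error of the bias at most 0.013 SD. Assumptions:

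- N = 100 or 200, half treated, left main prevalence 30%.
- Correlation 0, 0.3 or 0.6 among troponin, CK-MB, LVEF, EuroScore II, pain, left main, vessels and instability, with one third of that loading for age, sex and creatinine.
- Log-odds of IABP 0.5 or 1.0 for troponin, pain (per SD) and left main; half that for vessels; 0.3 for lower LVEF.
- Outcome shift 0.2 or 0.3 residual SD for troponin, lower LVEF, age, pain and left main; half that for vessels.

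The seven-covariate score was compared with a ten-covariate score that adds day-1 pain, left main and vessels. Bias in residual SD under overlap weights:

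| Case | Listed score | Ten covariates | Share remaining |
|---|---|---|---|
| 1. Day-1 pain equals the pain indication (best case) | 0.08–0.34 | about 0, by construction | about 0 |
| 2. Day-1 pain correlates 0.5 with it | 0.08–0.36 | 0.03–0.21 | 42–58% |
| 3. Case 2 plus unmeasured instability | 0.15–0.57 | 0.09–0.41 | 56–78% |

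Example from case 3 (N = 200, correlation 0.3, log-odds 1.0, shift 0.3): 0.364/0.551 = 66% remaining. With the score as a regression covariate or with 1:1 caliper matching, the listed score leaves 0.08–0.57 SD, of which 41–61% (case 2) and 57–79% (case 3) remains.

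False-positive rates in case 3, nominal 5%: at N = 100, 6–54% with the listed score and 4–32% with the extended one; at N = 200, 9–86% and 4–59%. In five scenarios checked by direction (500 runs each), false findings of harm under the listed score ran at 5–85% and false findings of benefit at 0–0.6%, against 2.5% per side. With strong proxies (correlation 0.6) and small effects, the listed score's rate is 3–4% in cases 1 and 2, which is no inflation.

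The simulation does not cover LCOS, mortality or the PCI covariate.

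**The case against.** The strongest reply is that the cohort is already selected for CABG, so multivessel disease and infeasible PCI may hardly vary; that LVEF, CK-MB and EuroScore II carry much of the remaining risk; and that the size of the bias rests entirely on assumed inputs. Much of this stands. It is why the anatomical variables are proposed only where they vary, and why the figures are illustration only. It does not reach rest pain, a primary indication for which a day-1 score is collected in both groups and not used.

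Several stronger readings are tempting, and the documents do not support them:

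- *The score adjusts for only one indication.* It names only one; partial adjustment through proxies is possible and cannot be checked.
- *Only the shock or arrest exclusion bears on an omitted indication.* The exclusions for mechanical complications and for angiography-caused injury may also bear on instability.
- *The bias favors IABP, or false positives reach 86% in this study.* Under the assumed effects the errors run towards harm, and no rate for this study can be derived.
- *The undefined hs-CTI value will adjust away the troponin effect.* Propensity scores conventionally use pre-treatment values, an admission value exists for both groups, and nothing applies the score to the mixed ANOVA. This is mainly a clarification.
- *The mixed ANOVA is affected in the same way.* A stable additive group difference does not bias its group-by-time term.

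A further fair point is that every consequence depends on a use of the score that the plan does not state. That belongs in the repair.

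**Conclusion.** The point holds as a mismatch between the stated reasons for treatment and the stated treatment model. It rests on the text, not on the simulation. The omission is certain; its effect is not. The magnitude depends on how far the omitted indications differ between groups, how strongly they affect outcome, and how well the listed covariates track them. The documents give none of these, and the effect could be negligible. The statement that the bias runs against IABP rests on the assumption that the omitted indications worsen outcome. It is worth fixing because the repair is cheap, with medium confidence that it would change a result. The repair reduces confounding by indication and should not be presented as removing it.

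**What to change.** Amend the Statistical Analysis section as follows:

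1. Add to the score the day-1 chest-pain score, taken before any IABP insertion in both groups, and describe it as a proxy for rest pain.
2. Add left main status and number of diseased vessels, abstracted from the existing angiogram, where these vary. Consider failed or infeasible PCI only if it varies and plausibly relates to outcome; a variable that drives treatment alone adds variance without reducing bias.
3. Keep the pre-placement pain score out of the main score, because it exists only in Group A and is taken at the point of insertion. Where an IABP precedes the day-1 score, treat that score as missing, or use the pre-placement score in a sensitivity analysis only.
4. Specify admission (pre-IABP) hs-CTI and CK-MB in both groups.
5. State which outcome comparisons use the score and how, and report standardized mean differences for the named and added covariates.
6. Name later recurrent pain and hemodynamic instability as residual confounders.

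**Cost.** A SAP edit and chart abstraction, with no new patient measurement. The score grows from 7 to 10 covariates, or 11 with PCI. In the simulation (10 covariates), the spread of the weighted estimate changed by −2% to +12%. Matching lost 3 to 18 percentage points of treated patients (34–73% matched, down to 29–68%). Mean squared error under weighting fell by 7–77%, 4–57% and 12–49% in cases 1 to 3. Across all three uses of the score it rose in 1 of 216 results, by 1%. Recording later pain and instability comparably in Group B would be new work and is not part of this repair.

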Patients who demonstrate a decline in hsCTI levels or experience recurrent chest pain attacks will undergo coronary artery bypass grafting (CABG). All surgical procedures will be performed by the same surgical team using a standardized approach. Surgical Approach: The surgeries will be conducted via a median sternotomy under cardiopulmonary bypass (CPB). Complete revascularization will be achieved with the application of an aortic cross-clamp (ACC), guided by the vascular anatomy identified during angiography. Assessment of Graft

Flow: Following the removal of the ACC and the termination of CPB, transit-time flow measurement (TTFM) will be employed to evaluate the graft flow rates, ensuring optimal surgical outcomes.

In the postoperative period, the following parameters will be recorded: Mechanical Ventilation Duration (MV): Measured in hours from the patient's admission to the intensive care unit (ICU) until the cessation of mechanical ventilation. Bleeding Volume: The total amount of bleeding in milliliters during the first 24 hours postoperatively. Length of Stay in the Intensive Care Unit (ICU): The duration (in days) from the postoperative phase until the patient is transferred to the general ward. Total Length of Hospital Stay (HS): The number of days from hospital admission to discharge. Low Cardiac Output Syndrome (LCOS): LCOS will be defined as the presence of the following criteria: Requirement for high-dose positive inotropic agents (e.g., adrenaline, dobutamine, or noradrenaline) administered via continuous infusion, lactic acidosis (lactate levels >4 mmol/L), persistent hypotension and decreased or absent urine output. In-Hospital Mortality: Any death occurring within 30 days postoperatively will be classified as in-hospital mortality.

Exclusion criteria

To ensure a homogeneous distribution of risk factors between the groups and to accurately evaluate the effect of IABP on troponin levels, the following patients will be excluded from the study:

• Patients requiring emergency surgery due to iatrogenic cardiac or coronary injuries caused by angiography.

• Patients with mechanical complications of acute myocardial infarction, such as chordae rupture or ventricular septal rupture.

• Patients undergoing surgery using the off-pump or pumped beating heart method.

- Patients with peripheral arterial disease.
- Patients with renal failure.
- Patients with a history of cerebrovascular accidents.

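### Infarct type (ST-elevation or not) enters neither the propensity score nor the repeated-measures comparison, so a different type mix between groups could be read as part of an IABP effect

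*Combined protocol and SAP*

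**What the plan says.** The opening paragraph takes in "Patients hospitalized due to acute myocardial infarction (AMI) and scheduled for coronary artery bypass grafting (CABG) surgery", with no split by ST-elevation, and such patients "will be included in this prospective observational cohort study". Treatment is not randomized: "Based on their clinical conditions, the patients will be categorized into two groups", with or without IABP. Under Preoperative IABP Application and Indications, the primary reasons for a pump "include elevated troponin levels and recurrent or persistent chest pain at rest". Further reasons listed there are hemodynamic instability, multivessel disease, left main disease, and anatomy where PCI failed or was not feasible.

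Under Laboratory Studies, "hsCTI levels will be checked at admission and subsequently every 24 hours for both groups until the patient undergoes surgery". EF is measured on the first day, early after surgery and at the one-month visit. The Exclusion criteria are introduced with the aim "To ensure a homogeneous distribution of risk factors between the groups and to accurately evaluate the effect of IABP on troponin levels". None of them concerns infarct type.

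In Statistical Analysis, "Differences between the IABP group and the control group regarding repeatedly measured outcomes will be analyzed using mixed ANOVA". The same section builds a propensity score by logistic regression, "incorporating the following covariates: age, gender, creatinine, CK-MB, hs-CTI levels, preoperative LVEF, and EuroScore II". It does not say whether the score is used for matching, weighting or adjustment, or for which outcomes. Infarct type is not named anywhere as a recorded variable, stratum, subgroup or covariate.

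**The concern.** In a cohort where clinical condition decides who gets the pump, measured baseline factors are the main protection against confounding. Infarct type is a basic way of dividing the enrolled population, and it could plausibly relate both to the indications for a pump and to the later course of hsCTI and EF. If it does, groups with different type mixes would differ on these outcomes even if the pump did nothing.

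The plan has two places where this could be handled. The propensity list is introduced as the covariates to be used, without any wording such as *for example*, and type is not on it. The mixed ANOVA, as written, compares IABP with control over time and nothing else. At stake is how a group difference in the serial hsCTI or EF results is interpreted. The stated aim of the exclusions, an accurate estimate of the pump's effect on troponin, makes hsCTI the clearer case.

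**Working it through.** **1. Figures in the plan.** The documents give no sample size, SD, effect size or type mix, so there is no figure to reproduce. All numeric inputs below are assumptions, except the 0.05 significance level in Statistical Analysis (sidedness not stated; two-sided assumed).

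**2. Difference in level at one draw, no adjustment, no pump effect.** Let g be the difference between groups in the ST-elevation share (assumed 0.10 to 0.30). Let r be the ratio of hsCTI between types at that draw (assumed 2 to 5). The ratio of geometric means between groups is exp(g × ln r).
- g = 0.10, r = 2: exp(0.10 × 0.693) = 1.07
- g = 0.20, r = 3: exp(0.20 × 1.099) = 1.25
- g = 0.30, r = 5: exp(0.30 × 1.609) = 1.62

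**3. What that ratio does not show.** On the log scale the spurious difference at every draw is g × ln r. If r is the same at all draws, the change from one draw to the next is g × (ln r − ln r) = 0. The group-by-time term is then unaffected (ratio 1.00), and only the group main effect carries the shift. Bias in the course needs r to change over time. If it goes from r1 to r2, the spurious ratio of changes is exp(g × ln(r2/r1)). Taking the extremes of the assumed range, r1 = 2 and r2 = 5, ln(2.5) = 0.916, which gives:
- g = 0.10: 1.10
- g = 0.20: 1.20
- g = 0.30: 1.32

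The plan does not state the analysis scale. On the raw scale a constant ratio would not cancel.

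**4. Effect on the false-positive rate, no adjustment.** Let δ be the difference between types in hsCTI change, in within-type SDs (assumed 0.3 to 1.0), with n per group and type shares pA and pB.
- Spurious difference: b = (pA − pB) × δ
- Variance in each group: v = 1 + p(1 − p)δ²
- SE = √[(vA + vB)/n]
- Two-sided rate: Φ(b/SE − 1.96) + Φ(−b/SE − 1.96)

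Worked case: n = 100, shares 60% and 40%, δ = 1.0. Then b = 0.20, v = 1 + 0.24 = 1.24 in each group, SE = √(2.48/100) = 0.157 and b/SE = 1.27. The rate is 0.245 + 0.001 = 0.246.

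| Type mix | b (SD) | Rate, 50 per group | Rate, 100 per group |
|---|---|---|---|
| 50% vs 50% | 0 | 0.05 | 0.05 |
| 60% vs 40% | 0.06–0.20 | 0.06–0.15 | 0.07–0.25 |
| 70% vs 30% | 0.12–0.40 | 0.09–0.44 | 0.13–0.73 |

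The last row is a 40-point gap, beyond the 10 to 30 points assumed in step 2. It should be read as an extreme.

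**5. How far a stand-in marker helps.** A linear-model simulation used 4,000 runs per setting, 100 per group, 70% vs 30%, δ = 0.8 and no pump effect. It adjusted for nothing, then for one marker that differs between types, then for type as well.

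| Adjustment | Spurious difference (SD) | False-positive rate |
|---|---|---|
| None | 0.32 | 0.56 |
| Marker differing by 0.5 SD between types | 0.30 | 0.51 |
| Marker differing by 1 SD | 0.26 | 0.40 |
| Marker differing by 2 SD | 0.18 | 0.21 |
| Infarct type in the model | about 0 | 0.05 |

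A marker reduces the bias according to how well it separates the types, but does not remove it. This uses the extreme mix and one marker. The score holds several markers that could work together, so the table shows the pattern rather than the size to expect here.

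**The case against.** The strongest reply is that no passage ties infarct type to the decision to place a pump. The listed indications are troponin, rest pain, instability, coronary anatomy and failed or infeasible PCI. Troponin, the most direct route by which type might act, is in the score, along with CK-MB, LVEF and EuroScore II. The score refers to hs-CTI levels in the plural without a time point, so it cannot be assumed to use only the admission value. Rest pain, left main disease and multivessel disease are named indications that are also not separate items on the list, so type is not the most obvious omission. Cardiogenic shock, cardiac arrest and mechanical complications are excluded, history is recorded, baseline characteristics are compared, and the covariates of the mortality regression are left open.

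Much of this stands. It makes the consequence conditional and lowers its weight. It does not close the gap, for three reasons. The listed markers may capture type only in part. The plan does not attach the score to the mixed ANOVA, so as written they do not protect that comparison at all. A baseline table can reveal an imbalance but does not correct it.

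A reader might infer that completing the propensity list would put the hsCTI and EF comparisons right. The text does not support that, because no link between the score and those comparisons is stated. A reader might also take 1.07 to 1.62 as the bias in the reported pump effect. Those ratios are unadjusted levels under assumed inputs, and a constant ratio drops out of group-by-time on the log scale.

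**Conclusion.** The omission is confirmed by the text: all acute infarctions are pooled, groups form by clinical condition, and neither the seven-item score nor the repeated-measures model accounts for infarct type. Harm follows only if the type mix differs between groups and the types differ in hsCTI or EF course. The documents give no figure for either, and with an equal mix the false-positive rate stays at 0.05.

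At a 20-point gap without adjustment, the illustration gives a false-positive rate of 0.06 to 0.25 across 50 to 100 patients per group and type differences of 0.3 to 1.0 SD. The residual after adjustment cannot be sized from the documents.

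A reader might go further and conclude that type is an established confounder here, or that hsCTI and EF are the comparisons on which the study rests. The documents support neither: assignment is not described in terms of type, and no primary outcome is named. The point is therefore a cheap improvement worth making, not a demonstrated error.

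**What to change.** 1. Record infarct type (ST-elevation or non-ST-elevation) at admission for every patient.
2. Add it to the propensity covariates.
3. Include type and type-by-time in the repeated-measures models for hsCTI and EF. This is the step that changes those comparisons; step 2 alone would not.
4. Show the hsCTI course by type within each group, as a descriptive display.

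The cost is one baseline field, one extra propensity term and a few degrees of freedom in each repeated-measures model. For EF, with three measurement times, that is 1 for type plus 3 − 1 = 2 for type-by-time, so 3 in all. For hsCTI it depends on how many draws are analysed. With no sample size stated, the sponsor should check that the models can carry these terms.
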